1.2 OVERALL RATIONALE FOR THE STUDY

The GPEI acknowledged that additional efforts are urgently needed to address cVDPV2 circulation. The 2022-2026 strategy largely relies on the scale-up of nOPV2 use, but also includes as a pivot the improvement of vaccination campaign planning and execution to increase vaccination coverage and avoid “zero-dose” children¹⁵. The current recommendation is to complete 2 large (>90% of children vaccinated) vaccination campaigns within 8 weeks of the first laboratory sequencing result, but their duration might be extended to reach missed children. In addition, short-interval campaigns may be put in place, for example with intervals between 2 mOPV2 doses reduced to 1 week, under certain circumstances such as the presence of multiple circulating polioviruses or short window of access to the target population, similar to the experience with mOPV2¹⁶.

In a phase IV randomized, controlled study in Bangladesh, the immunogenicity of 2 doses of mOPV2 when administered at varying intervals of 1 week and 2 weeks was assessed and compared to the standard 4-week interval. Between December 7th, 2015, and January 5th, 2016, 760 infants were randomized to receive 2 mOPV2 doses at intervals of 1 week (n=191), 2 weeks (n=191), 4 weeks (n=188), or 4 weeks plus IPV (n=190). Immune responses after 2 mOPV2 doses were observed in 161 (93%) of 173 infants with testable serum samples in the 1-week group, 169 (96%) of 177 in the 2-week group, and 176 (97%) of 181 in the 4-week group. One-week and 2-week intervals between 2 mOPV2 doses were non-inferior to 4-week intervals; the difference in seroconversion rate between the 1-week interval group and the 4-week interval group was -4.2 (90% confidence interval [CI]: -7.9; -0.4), and it was -1.8% (90% CI: -5.0; 1.5) in the 2-week interval group compared to the 4-week interval group¹⁷.

To date, no data exist on the immunogenicity of nOPV2 when administered at shorter intervals. It is important to investigate shorter intervals of administration, as reducing the interval between 2 administrations could contribute to the effectiveness of the vaccination campaigns.

1.3 RISK BENEFIT ANALYSIS

1.3.1 *Potential Risks*

The nOPV2 vaccine being used in the proposed study was designed to be more genetically stable and less likely to revert to a neurovirulent phenotype than the Sabin mOPV2, and this has been confirmed in preclinical and clinical assessments. The attenuations do not appear to affect the immunogenicity of the vaccine.

In the M5 study⁸, solicited adverse events (AEs) in children and infants included abnormal crying, drowsiness, fever, irritability, loss of appetite, and vomiting. No SAEs or important medical events (IMEs) considered related to vaccination were reported for nOPV2. Severe AEs considered related to vaccination were reported, the most frequent of which was abnormal crying. All were transient, usually resolving within 3 days. No clinically relevant differences were observed in SAEs, AEs or IMEs related to vaccination between nOPV2 and mOPV2 groups. SAEs that entailed hospitalization (mild bronchitis and moderate pneumonia) were not considered related to study vaccine. There were no AEs that led to death, to withdrawal, or to permanent study discontinuation.

The attenuated strains of poliovirus multiply in the gut. The fecal excretion of the vaccine virus may persist for several weeks, especially in unprotected populations, and may also be transmissible to the contacts of the vaccinees contributing to the herd immunity against polio. In populations with low immunity, a close contact with a recently vaccinated subject may very rarely be at risk of developing paralytic poliomyelitis caused by the vaccine (VAPP). Clinical data from the Phase I and Phase II adult studies (M4a and M4) and the Phase II pediatric study (M5) support the improvements in genetic and phenotypic stability of the nOPV2 vaccine, with no meaningful increase in neurovirulence observed⁶⁻⁸. Genetic stability analyses do not suggest any anticipated increase in the likelihood of VAPP with the vaccine which will be used in this study.

1.3.2 *Potential Benefits*

Infants who will be vaccinated with nOPV2 in this study will potentially develop high levels of immunity against poliovirus type 2. Indeed, a key benefit of nOPV2 is the intestinal immunity (in addition to humoral immunity) against type-2 poliovirus disease which is conferred through vaccination by the oral route.

Given the global public health need of a safer alternative to mOPV2, this study is important in establishing immunological responses to nOPV2 when administered at shorter intervals. If the data are supportive, it will assist in the design of a new polio vaccination strategy that will enhance the effectiveness of the vaccination campaigns to prevent emergence and further spread of cVDPV2 and generation of type 2-related VAPP cases.

2. STUDY OBJECTIVES

2.1 PRIMARY OBJECTIVE

The primary objective of the study is to determine if the immune response (seroconversion rate to poliovirus type 2) 28 days following administration of 2 doses of nOPV2 given at different intervals of 1 week or 2 weeks is non-inferior to that following the standard 4-week interval in infants.

2.2 SECONDARY OBJECTIVES

The secondary objectives of the study are:

- To assess and compare the immune response to poliovirus type 2 (geometric mean and median neutralizing antibody titers, fold-rise and seroprotection rate) 28 days following administration of 2 doses of nOPV2 given at shorter intervals of 1 week or 2 weeks relative to the standard 4-week interval.
- To assess the immunogenicity to poliovirus type 2 (geometric mean and median neutralizing antibody titers, fold-rise, seroconversion rate and seroprotection rate) 1, 2, or 4 weeks following 1 dose of nOPV2.
- To assess the safety expressed as incidence, severity and causality of SAEs, solicited AEs, unsolicited AEs and any IMEs following administration of nOPV2 given at shorter intervals of 1 week or 2 weeks or at the standard 4-week interval.

2.3 EXPLORATORY OBJECTIVE

To compare the immunogenicity to poliovirus type 2 (geometric mean and median neutralizing antibody titers, fold-rise, seroconversion rate, and seroprotection rate) following 2 doses administered 1 week apart relative to 2 weeks apart.

3. STUDY ENDPOINTS

3.1 PRIMARY ENDPOINTS

The primary endpoint is the cumulative seroconversion rate of type 2 polio neutralizing antibodies 28 days following administration of 2 doses of nOPV2 in 1-, 2-, and 4-week intervals to infants 6 to 8 weeks of age.

Seroconversion is defined as seropositive (titer $\geq 1:8$) in those initially seronegative, or among those initially seropositive, as a minimum 4-fold higher titer (and seropositivity) than that which is expected due to maternal antibodies, using an exponential model to estimate the maternally-derived antibody titers at post-vaccination time points from the pre-vaccination time point, assuming a half-life of 28 days.

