This study will be conducted in the Dominican Republic, and it is not anticipated that immune response rates will be lower than those observed in the previous mOPV2 study. Therefore, with a conservative assumed cumulative 2-dose seroconversion rate of 85% in each group, 270 evaluable subjects per group are required to demonstrate non-inferiority of each of the shorter intervals to the standard interval, using margin 10%, two-sided Type I error rate of 5%, and requiring 90% power. This will be further increased to 300 per group to account for loss to follow-up or other loss from the evaluable population.

Immunogenicity

At each pre-and post-vaccination time point where neutralizing antibody titers are obtained:

- Cumulative seroconversion rates (with 95% exact CIs) will be computed from Day 0 at post-vaccination time points. Seroconversion is defined as seropositive (reciprocal titer ≥ 8) in those initially seronegative, or among those initially seropositive, as a minimum 4-fold higher titer (and seropositivity) than that which is expected due to maternal antibodies, using an exponential model to estimate the maternally-derived antibody titers at post-vaccination time points from the pre-vaccination time point, assuming a half-life of 28 days.
- Seroprotection rates (with 95% exact CIs) will be computed
- Geometric mean and median neutralizing antibody titers (with 95% CIs) will be computed
- Plots of the reverse cumulative distribution of antibody titers will be generated for each group.
- Geometric mean fold-rise (with 95% exact CIs) will be computed

Safety

Safety parameters will be tabulated and analyzed descriptively.

Analyses described below will be performed for solicited and unsolicited AEs by severity as well as for SAEs and IMEs. Events will only be considered as solicited AEs if onset occurs within 7 days of a vaccine administration. All events with onset between Days 8 and 28 post-vaccination will be considered unsolicited AEs, with only SAEs and IMEs recorded after 28 days post-last-vaccination.

The original terms used in the designated sections of the electronic case report forms by Investigators to identify unsolicited AEs will be fully described and coded according to the Medical Dictionary for Regulatory Activities.

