3.2 SECONDARY ENDPOINTS

Immunogenicity:

- Geometric mean and median titers of type 2 polio neutralizing antibodies Day 0 and 28 days after the second dose of nOPV2 when administered 1, 2, or 4 weeks apart.
- Cumulative fold-rise (from Day 0) in titers of type 2 polio neutralizing antibodies 28 days after the second dose of nOPV2 when administered 1, 2, or 4 weeks apart. Cumulative fold-rise will be computed relative to the expected level of maternally-derived antibody titers in accordance with the seroconversion definition.
- Fold-rise (from post-dose-1 level) in titers of type 2 polio neutralizing antibodies 28 days after the second dose of nOPV2 when administered 1, 2, or 4 weeks after dose-1. This fold-rise will be computed from the level attained following the first dose, with the pre-dose-2 serum sample.
- Seroprotection rate to poliovirus type 2, at Day 0 and 28 days after the second dose of nOPV2 when administered 1, 2, or 4 weeks apart.
Seroprotection rate is defined as the percentage of subjects with type 2-specific antibody titers $\geq 1:8$.
- Geometric mean and median titers of type 2 polio neutralizing antibodies 1, 2, and 4 weeks after 1 dose of nOPV2.
- Fold-rise in titers of type 2 polio neutralizing antibodies 1, 2, and 4 weeks after 1 dose of nOPV2. This fold-rise will be computed relative to the expected level of maternally-derived antibody titers in accordance with the seroconversion definition.
- Seroconversion rate 1, 2, and 4 weeks after 1 dose of nOPV2.
- Seroprotection rate 1, 2, and 4 weeks after 1 dose of nOPV2.

Safety:

- Incidence of SAEs and IMEs as of the informed consent signature date and throughout the study period in all groups by severity and causal association.
- Incidence of mild, moderate and severe solicited AEs (fever, vomiting, abnormal crying, drowsiness, loss of appetite, diarrhea and irritability) for 7 days after each dose of study vaccine in all groups.
- Incidence of mild, moderate and severe unsolicited AEs for 28 days after each dose of study vaccine by causal association in all groups.

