8.2 IMMUNOGENICITY

8.2.1 *Immunogenicity Variables*

Blood samples for the determination of neutralizing type 2 poliovirus antibodies will be taken at the time points specified in the Time and Events Schedules. Neutralizing antibodies against poliovirus will be determined using a sero-neutralization assay.

Detailed descriptions of the collection, handling, transport and processing of the blood samples will be included in the laboratory manual.

Samples that remain after protocol-specific assessments have been performed may be used for further exploratory work on polio, including cryofreezing for future immunological studies. No human DNA or RNA analysis will be performed.

8.2.2 *Immunogenicity Criteria*

For an overview of endpoints, see Section 3.

The following endpoints will be based on neutralizing type 2 poliovirus antibody titers:

- Seroconversion: defined as seropositive (titer $\geq 1:8$) in those initially seronegative, or among those initially seropositive, a minimum 4-fold higher titer (and seropositivity) than that which is expected due to maternal antibodies, using an exponential model to estimate the maternally-derived antibody titers at post-vaccination time points from the pre-vaccination time point, assuming a half-life of 28 days. Seroconversion will be computed from Day 0 for all subjects.
- Seroprotection: defined as poliovirus serotype-specific titers $\geq 1:8$.
- Geometric mean and median titers.
- Geometric mean fold-rise

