9. STUDY TERMINATION/COMPLETION

9.1 STUDY COMPLETION

9.1.1 Subject Completion

A subject will be considered to have completed the study if all study-related procedures have been completed for them 28 days after the last study vaccination (i.e, Day 35 [Group A], Day 42 [Group B] or Day 56 [Group C]) and they are not withdrawn before the final study safety follow-up 6 months after their last study vaccination (i.e, Day 187 [Group A], Day 194 [Group B] or Day 208 [Group C]).

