Comparisons of GMTs will arise from geometric mean titer (GMT) ratios computed via a linear model of the \log_2 titers which incorporates left/right censoring at LLOQ/ULOQ. With the exception of the comparison of baseline immunity, a separate model will be fit for each comparison, limited to the groups involved in the comparison. For baseline immunity, a global F-test for a difference will be conducted and, if significant at level 0.10, the model will be used to produce pairwise comparisons of each group. The reverse-transformed two-sided 95% CI for the GMT ratio will be paired with the p-value corresponding to the F-test for a difference between groups. A difference between groups will be indicated if the CI excludes a GMT ratio of 1.

Median titers will be analyzed on the \log_2 scale, and paired with two-sided 95% bootstrap CIs. A difference between groups will be indicated if the interval excludes a difference of 0.

Fold-rises will be compared using standard normal distribution-based two-sample methodology on the \log_2 scale, followed by a reverse transformation. If an excess of titers reaches assay limits of quantitation, subgroup analyses will be conducted among those subjects with samples within the quantifiable range. A difference between groups will be indicated if the two-sided 95% CI for the ratio of geometric mean fold rises (reverse-transformed difference of differences) excludes a value of 1.

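### The maternal-antibody correction is read on Day 35, 42 or 56 depending on arm, so the between-arm cumulative fold-rise test, and to a lesser extent seroconversion, partly measures elapsed time

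*Combined protocol and SAP*

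**What the plan says.** Section 3.1 defines seroconversion in two branches. Initially seronegative infants need a titre of at least 1:8, with no decay term. The rule for the others is "among those initially seropositive, as a minimum 4-fold higher titer (and seropositivity) than that which is expected due to maternal antibodies", and the analyst is to "estimate the maternally-derived antibody titers at post-vaccination time points from the pre-vaccination time point, assuming a half-life of 28 days". Section 8.2.2 fixes the origin: "Seroconversion will be computed from Day 0 for all subjects".

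The sample 28 days after dose 2 falls on a different day in each arm. Section 9.1.1 gives "Day 35 [Group A], Day 42 [Group B] or Day 56 [Group C"], and Tables 1 to 3 agree.

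Section 3.2 carries the same reference into a secondary endpoint: "Cumulative fold-rise will be computed relative to the expected level of maternally-derived antibody titers in accordance with the seroconversion definition". Section 10.1.4 compares it formally: "A difference between groups will be indicated if the two-sided 95% CI for the ratio of geometric mean fold rises" excludes 1. A second fold-rise is based on the post-dose-1 titre: "This fold-rise will be computed from the level attained following the first dose, with the pre-dose-2 serum sample". That sample is drawn 7, 14 or 28 days after dose 1.

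For the primary endpoint, section 10.1.4 declares non-inferiority if the lower Miettinen-Nurminen bound exceeds −10%. No section sets a common reference day, adjusts for elapsed time, or plans a sensitivity analysis for it.

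**The concern.** The arms differ by design in how long after Day 0 the final sample is taken. A reference that halves every 28 days is therefore lower in Group C than in A or B, and a fixed 4-fold multiple of it is an easier bar in C. Two infants with the same Day 0 titre and the same final titre can be scored differently because of their arm.

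Two results are exposed. The cumulative fold-rise comparison can report a deficit for the shorter intervals when titres are the same, and so contradict the GMT comparison made on the same samples. The primary seroconversion difference can be pulled down in A and B, using part of the 10-point margin for something that is not vaccine response.

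**Working it through.** **1. The plan's own figure.** Inputs from section 10.2: 85% in each group, margin 10 points, two-sided 5%, power 90%. n = 2 × 0.85 × 0.15 × (1.960 + 1.282)² / 0.10² = 268, against 270 stated. At 270 the SE is √(2 × 0.85 × 0.15 / 270) = 0.0307, and power is Φ(0.10/0.0307 − 1.960) = 90.2%. The figure reproduces.

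**2. The bar by arm.** Let T0 be the Day 0 titre and R = T0 × 2^(−t/28) the expected maternal titre on day t.

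| | A (Day 35) | B (Day 42) | C (Day 56) |
|---|---|---|---|
| R / T0 | 0.420 | 0.354 | 0.250 |
| Bar, 4R / T0 | 1.68 | 1.41 | 1.00 |
| Bar if T0 = 64 | 108 | 91 | 64 |

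With T0 = 64, a final titre of 80 seroconverts only in C.

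**3. Allowing for residual maternal antibody.** If vaccine-induced antibody V adds to the residual, V + R ≥ 4R becomes V ≥ 3R. The required V is 1.26, 1.06 and 0.75 times T0, so the same vaccine response is still scored lower in A and B.

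**4. Fold-rise shift.** For identical T0 and final titre, the ratio to C is 2^((t−56)/28): 0.59 for A (−0.75 log2) and 0.71 for B (−0.50 log2). In the additive model at V = T0 the ratios are 0.68 and 0.77, and they approach 0.59 and 0.71 as V grows. The exploratory A-versus-B comparison shifts by 0.25 log2.

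The plan does not say whether the reference is decayed for seronegative infants. If it is decayed only for a seropositive fraction f, the mean A–C shift is 0.75f. For f = 0.50 the ratio is 2^(−0.375) = 0.77; for f = 0.77 it is 2^(−0.5775) = 0.67.

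**5. Chance of a spurious difference.** SE = SD × √(2/270). The SD of log2 fold-rise is assumed (2.5 to 3.5), as is f; the documents give neither. Titres are identical across arms.

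| Decayed reference applies to | A vs C | B vs C |
|---|---|---|
| every infant | 70–94% | 38–64% |
| 77% | 48–77% | 25–43% |
| 50% | 24–41% | 13–21% |

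**6. Primary endpoint.** Simulation with identical vaccine-induced titres in all arms. Assumptions, none in the documents: log2 SD 2 for maternal and 2.5 for vaccine-induced titre, correlation −0.3, and the mean vaccine response set to give C the stated rate. Power = Φ((Δ + 0.10)/SE − 1.960), with SE² = [p_C(1−p_C) + p_A(1−p_A)]/270.

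| Rate in C | Vaccine take | Seropositive at Day 0 | A − C (points) | Power for A |
|---|---|---|---|---|
| 85% | 99% | 50–77% | −4.0 to −5.0 | 46–34% |
| 85% | 90% | 50–77% | about −2.3 to −2.5 | 69–66% |
| 85% | 87% | 50–77% | about −1.2 | about 81% |
| 85% | 87% | 25% | −0.9 | 83% |
| 95% | 99% | 50–77% | about −2 | about 97% |
| 97% | 99% | 50–77% | about −1.2 | over 99.9% |

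For B minus C at 85% and 99% take, the shift is −2.6 to −3.2 points.

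A cruder model holds the measured titres, not the vaccine responses, equal across arms. With log2(titre/T0) SD 2 to 4 and 25–100% seropositive it gives −1.2 to −10.4 points at 85% and −0.6 to −5.2 at 95%. Its extremes need the narrowest spread and every infant seropositive, and it ignores the extra residual on Day 35. It is not relied on here, but it shows how far the size depends on inputs.

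**7. A common bar.** Requiring 1.68 × T0 in every arm is 4.0, 1.68/0.354 = 4.8 and 1.68/0.250 = 6.7 times the expected level in A, B and C, so at least 4-fold everywhere. In the step 6 model with C at 85%, it favours A over C by about 0.3 to 1.4 points.

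**The case against.** The strongest reply is that using elapsed time is right in principle: more maternal antibody does remain on Day 35 than on Day 56, so an identical measured titre is not an identical vaccine response. That stands, and it is why the additive fold-rise ratio at V = T0 is 0.68 and not 0.59. It does not remove the asymmetry, because multiplying the residual by 4 over-corrects for it (step 3).

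Second, the primary bias is conservative. A reader might infer that it threatens the validity of a non-inferiority claim. It does not: it makes the claim harder to reach and cannot create it. The risk is a false failure.

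Third, a reader might infer that power for A collapses to 34–46%. That needs a true rate of 85%, which section 10.2 calls conservative against the 93.1–97.2% seen with mOPV2, together with an assumed 99% take. Lower take at the same rate gives about 66–83%, and at 95% or more the step 6 model keeps power near 97% or above.

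Fourth, the fold-rise test need not be a test against a GMT ratio of 1.68. That reading holds only if the reference is decayed for every infant, which the plan leaves open.

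Fifth, uncorrected GMT, median and seroprotection comparisons are planned, as is a subgroup by baseline immune status, and full methods are deferred to the SAP. These help interpretation. None replaces the decision rule for fold-rise.

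Finally, a reader might infer that Group A's rise from the post-dose-1 sample contains most of the dose-1 response. The documents give no post-dose-1 kinetics, so only the weaker statement holds: the reference sample is taken at a different time in each arm.

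**Conclusion.** The arm-dependent bar (1.68, 1.41 and 1.00 times Day 0 titre) follows from the protocol's definitions without outside input, and nothing in the plan corrects it.

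The clearest harm is secondary. The between-arm cumulative fold-rise test partly tests elapsed time, with a chance of a spurious A–C difference of about 24% to 94%, conditional on the assumed SD, the seropositive fraction and the unstated handling of seronegative infants.

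For the primary endpoint only initially seropositive infants near the bar are affected, and the direction is against the shorter intervals. Size depends on baseline seropositivity, take and titre spread, which the documents do not give: roughly −1 to −5 points for A minus C if C is 85% (power about 83% to 34%), and about −1 to −2 points if C is 95–97% (power about 97% or more in the additive model). The direction is firm; the size is not. This is a should-fix: the primary definition can stay, but the fold-rise comparison should not be tested as written.

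**What to change.** Before the SAP is finalised:

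1. Make the between-arm secondary comparison on post-dose-2 log2 titre adjusted for Day 0 titre, using the censored linear model already in section 10.1.4. Report the decay-corrected and the post-dose-1-based fold-rises within arm only, because their reference times differ by arm.
2. Keep the protocol seroconversion definition as primary. Pre-specify a sensitivity analysis of the non-inferiority comparison in which initially seropositive infants in every arm must reach at least 1.68 times the Day 0 titre and be seropositive. Report both results.
3. State how the expected maternal level is set for infants below the LLOQ, and whether nominal or actual days are used. A 2-day delay, which the visit windows allow, moves the bar by about 5% (1.68 to 1.60 in A).

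The cost is SAP wording and one derived variable, with no new samples or visits. The downside should be stated in the SAP: both changes leave residual maternal antibody slightly favouring the shorter intervals (about 0.3 to 1.4 points for the common bar under the step 6 assumptions). That is the anti-conservative direction for non-inferiority, so the common-bar result supports interpretation and does not replace the primary test.
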